3. To examine whether a change in trajectory of language development can be seen after the placebo group goes on AFQ056 in the open label extension period.
4. In the absence of drug effect, to examine the trajectory of the effects of the language intervention over a longer time period (14 months).
5. To examine the trajectory of the ERP biomarker performance across a longer time period of development, and sensitivity to both the drug and language intervention.

Due to study drug expiration in August 2021, the length of the open label extension may be shortened depending upon the date the subject is consented. For subjects consented prior to June 2019, the open label extension period will be 8 months allowing the entire 21-month protocol to be completed. For any subject that is consented in or after June 2019 the open label extension period may be shortened on a sliding scale for those enrolled after June 15, 2019, such that their treatment including weaning, if necessary, will end before August 31, 2021, with the exact length of the stable treatment period in the extension being determined by how long after June 15 they enroll and what dose of drug they are receiving in the open label treatment period. The total duration of the stable treatment for those enrolled after June 15, 2019 will range from 6 months to no open label extension, depending on the number of months after June 15, 2019 the subject is enrolled into the study.

Auditory event-related potentials (ERP), is a CNS measure that is significantly abnormal (both amplitude and habituation) in FXS, has shown improvement in habituation in an oddball paradigm in a prior pilot trial of minocycline in FXS, and would be expected to relate to language processing and learning. The ERP biomarker will be utilized in this protocol as an assay of direct effects of AFQ056 and/or language intervention on CNS activity. The prolonged time course of the study should allow the biomarker to be linked to developmental parameters over time so that its value as a predictive marker for long-term clinical effects of interventions in FXS can be determined. A marker of CNS activity that is linked to clinical outcomes is badly needed in the field and would be a tremendous resource for future interventions research.

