After 8 month assessments in the placebo-controlled phase (including 6 months of language intervention), all subjects will enter the extension and be treated with active drug according to the same schedule as in the placebo-controlled phase. All subjects will be dosed with 25 mg BID of unblinded AFQ056 upon completion of the 8 month visit, followed by 2 months of flexible dose forced-titration to the MTD of the dose levels available in the protocol (dose adjustments to be done as described above for the placebo-controlled period for the flexible dose forced-titration). This will be followed by a period of stable treatment. The length of stable treatment will be dependent upon how long after June 15, 2019 the participant enrolls and what dose of drug they are receiving in the open label treatment period. The total duration of the stable treatment for those enrolled after June 15, 2019 will range from 6 months to no open label extension, depending on the number of months after June 15, 2019 the subject is enrolled into the study.

Some subjects will have an acute dose decrease if they were on 50-100 mg BID of active drug in the initial phase but experience from the PK study suggests that children can come off AFQ without withdrawal symptoms and the dose decrease and titration in the open label extension are unavoidable to maintain the blind of the study through the completion of the placebo-controlled period by the final participant. Subjects will continue the language intervention through the extension phase. The open-label extension will allow all children a period of active drug exposure to make recruitment feasible, despite the long placebo period. It will also allow an assessment of more long term-effects of the language intervention and its impact on the ERP and eye tracking biomarker outcomes and other developmental and behavioral outcomes, will allow examination of the trajectory of the language intervention going from placebo to drug treatment in a blinded setting, and will furthermore allow additional long-term safety data to be collected on a larger cohort of children exposed to AFQ056. A diagram of the study design is provided below in Figure 2.

Figure 2. Effects of AFQ056 on Language Learning in Young Children with Fragile X Syndrome (FXS) – Protocol Design

AFQ056 for Language Learning in Children with FXS

Version v15

Version date 02/03/2021

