### **Language Intervention**

The language intervention will be administered by a trained language specialist (training to be completed with videotapes and practice activities to reach fidelity at initiation of the study through at-home synchronous video conferencing sessions). Initial administration of the parent education session of the intervention will be done around the time of the 2 month visit using a didactic education session and delivery of the intervention will be started at that visit. The intervention will subsequently be delivered to the parent by a speech-language clinician through weekly clinician coaching, homework, and feedback sessions.

The entire intervention will be delivered to the parent in the home or at scheduled study visits through the use of a laptop computer equipped with distance video-teleconferencing software. Coaching, homework, and feedback sessions will occur weekly for 4 months, then monthly for the remainder of the study through the final two months of the placebo-controlled portion and the subsequent open-label extension.

The parent will be trained in stepwise fashion to administer the language intervention to the child over the entire subsequent course of participation in the study.

SLPs will set up 1-2 distance technology training sessions with the subject family between month 1 and month 2 (visits 4 and 5). During the call, SLPs will review the technology procedures, work with the parent/primary caregiver to set up the intervention environment and work on setting up the equipment as necessary for the language intervention. These practice calls will need to be completed prior to visit 5 (month 2), after which the language intervention will begin. Please refer to the SLP Training Manual for more details.

The didactic sessions will involve power point presentations with video examples of implementation. The coaching sessions will involve real-time instruction and feedback to the parent (via MacBook computers and Bluetooth “bug in the ear” technology both provided to the parent at the 1 month visit) while the parent interacts with the child in a play-based format. The

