The study number for the subject and study visit number will be added to the label by the coordinator at each study visit when the study drug is given to the subject. Study drug will be dispensed to subjects at all study visits after screening, until the Follow Up visit, after which no more study drug will be provided. From the month 8 visit on, study drug will no longer be blinded and all subjects will receive active drug. Drug dispensed at the month 8 visit and after will be labeled as AFQ056 and will contain the same information as the AFQ056/placebo labels for bottles dispensed up to month 8. Amount of study drug dispensed during flexible dosing periods will be calculated to accommodate any possible dose increases that would occur prior to the next study visit. All bottles of study medication including empty, partially used and unused bottles will be returned to the study site at each visit, and a new set of bottles will be dispensed.

Study drug will be received at the study site by a designated person, handled and stored safely and properly at the site pharmacy or other designated location, and kept in a secured location to which only the Study pharmacist and staff, site Investigator and designated staff have access. Upon receipt, the study drugs will be stored according to the instructions specified on the drug labels. Storage conditions will be adequately monitored and temperature in the area in which the study drug is stored will be controlled, monitored and recorded, at a minimum on a daily

basis. Appropriate temperature logs will be maintained. For more details, please refer to the Study Medications/Central Pharmacy section of the Manual of Operations.

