The LMM is estimated with maximum likelihood, which provides unbiased estimates under an ignorable missing data mechanism. The likelihood ratio test (LRT) will be used to evaluate  $H_0$  by comparing the full model of Equation 1 with a reduced model that omits  $\gamma_1$  (cf. Equations 1a and 1b). There is a one-parameter difference among the models, and the LRT test statistic,  $\chi^2_1$ , has an asymptotic chi-squared distribution. Evidence of treatment efficacy is provided when  $\chi^2_1 > \chi^2_{1,1-\alpha}$ , the latter being the upper  $1 - \alpha$  chi-squared quantile, which leads to the rejection of  $H_0$ . An alternative index of efficacy relevant for this proof-of-concept proposal is the difference in Akaike's information criterion (AIC) among the models. The AIC is an unbiased estimator of  $-2$  times the mean expected log likelihood, and the difference in AIC among two models is their statistical distance. Suppose AIC(full) is the sample AIC for the estimated full model of Equation 1, and AIC(reduced) is that of the reduced model that omits  $\gamma_1$ . Smaller AIC values indicate better statistical fit, so evidence of efficacy is provided when  $\Delta\text{AIC} = \text{AIC}(\text{reduced}) - \text{AIC}(\text{full}) > 0$  because the model with  $\gamma_1 > 0$  has better fit than the model with  $\gamma_1 = 0$ .

AFQ056 for Language Learning in Children with FXS

Version v15

Version date 02/03/2021

The open label phase of the study has both groups receiving treatment (see Figure 2). Change during this phase will also be analyzed using a separate LMM. Focus will again be on the PL and TX slope difference, but the intercept difference will be non-zero ( $\square_0 \neq 0$ ) due to the possibility of a treatment effect in the treatment phase (i.e., an inequality at the end of the treatment phase). The group slope difference might not be statistically significant if the PL group catches up to the TX group during the open label phase. Therefore, the open label phase analysis is considered exploratory.

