- Longitudinal analysis to determine whether the rate of change in language, functional, or biomarker responses in the group assigned to placebo will be lowest during the first 6 months of the study (Screening to visit 5/month 2), higher in the next 6 months with the language intervention (visit 5/month 2 to visit 9/month 8), and highest in the final 8 months with both the language intervention and AFQ056 treatment (visit 9/month 8 to visit 14/month 16) – with inflection points at visit 5/month 2 when the language intervention is started and visit 9/month 8 when AFQ056 is started.
- Analyses of change from baseline at the 2 month visit (visit 5) will be evaluated for all clinical and biomarker outcomes, to determine if effects of drug alone can be identified before the language intervention is initiated. Likewise analyses of change from baseline and from the final visit before weaning treatment with AFQ056 (16 month visit, visit 14) at the Follow Up visit (visit 15) will be evaluated for all clinical and biomarker outcomes, to determine if regressive effects of coming off drug are evident. Covariates in the analyses will be medication (coded as a factor with a small number of levels), age, and additional variables that are shown to be imbalanced through unlucky randomization.

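### Under the plan's own slope model the open-label arm comparison says nothing about efficacy, and the placebo-arm comparison is partly confounded with the coaching reduction at month 6

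*Combined protocol and SAP*

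**What the plan says.** Section 2.1 lists among the purposes of the extension: "To examine whether a change in trajectory of language development can be seen after the placebo group goes on AFQ056". Objective 1.4.4 likewise asks whether the rate of change improves further once AFQ056 is added to the language intervention.

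Two analyses bear on this.

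- **Between arms (Section 9.6.1).** "The open label phase of the study has both groups receiving treatment (see Figure 2"). A separate mixed model is fitted to this phase: "Focus will again be on the PL and TX slope difference, but the intercept difference will be non-zero". The text then says "The group slope difference might not be statistically significant if the PL group catches up to the TX group during the open label phase", and for that reason labels the analysis exploratory.
- **Within the placebo arm (end of Section 9.6.1, and Section 9.6.3).** Progress on placebo alone, on placebo with the language intervention, and on AFQ056 with the language intervention is compared, "with inflection points at visit 5/month 2 when the language intervention is started and visit 9/month 8 when AFQ056 is started".

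Section 5.1 sets the coaching schedule: "Coaching, homework, and feedback sessions will occur weekly for 4 months, then monthly for the remainder of the study". Weekly coaching starts at month 2, so the change falls at month 6.

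On blinding, Section 3 describes the "trajectory of the language intervention going from placebo to drug treatment in a blinded setting", whereas Section 5.2 says "From the month 8 visit on, study drug will no longer be blinded".

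**The concern.** The extension is meant to show whether starting AFQ056 changes the former placebo group's rate of progress. The between-arm analysis sets two treated arms side by side and drops the blinded-phase slopes that would give a null difference a meaning. A reader who follows the catch-up sentence could take similar slopes as a sign that the placebo arm had caught up, when similar slopes are also what an inert drug produces.

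The within-arm analysis does address the question. However, its middle period mixes weekly and monthly coaching while its last period is all monthly, and nothing in Section 9.6 separates the two. A real gain could be masked by the coaching change. Knowing that the child is now on active drug could push the other way.

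**Working it through.** **Inputs.** Equation 1 (Section 9.6.1): blinded slopes β₁ (placebo) and β₁ + γ₁ (AFQ056). Weighted communication score at months 2, 4, 6, 8, 10, 12 and 16 (Section 6.3.9). Combined sessions: 48 in months 2–5 and 33 in months 6–17 (Sections 5.1 and 5.4).

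**1. Session counts.** 16 weeks × 3 session types = 48. 11 monthly rounds × 3 = 33 (12 rounds would give 36). 41/48 = 85% and 25/33 = 76%, as stated.

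- Step at month 6: 48/4 = 12 per month to 33/11 = 3 per month, fourfold (4.4-fold if the 33 are spread over 12 months).
- Periods actually compared: (48 + 2 × 3)/6 = 9 per month in months 2–8 against 3 afterwards, threefold.

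**2. Open-label contrast, AFQ056 minus placebo slope.**

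- Inert drug: β₁ − β₁ = 0.
- Drug acting as in Equation 1: (β₁ + γ₁) − (β₁ + γ₁) = 0, for any γ₁.
- Catch-up in level: the month-8 gap is 8γ₁. To close a fraction c of it linearly by month 16, the placebo arm needs extra slope c × 8γ₁/8 = cγ₁, so the difference is −cγ₁: −0.25γ₁, −0.50γ₁ and −γ₁ for c = 0.25, 0.5 and 1. Catch-up complete by month 12 gives −0.97γ₁ (least squares at months 8, 10, 12 and 16).

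**3. Placebo-arm contrast.** Let w and m be the learning rates under weekly and monthly coaching. Relative to month 2, expected scores at months 2, 4, 6 and 8 are 0, 2w, 4w and 4w + 2m. Centred times are −3, −1, 1 and 3, with sum of squares 20:

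slope = [−2w + 4w + 3(4w + 2m)]/20 = 0.7w + 0.3m.

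The months 8–16 slope is m + γ. The contrast is therefore γ − 0.7(w − m). If month 6 were left out, as in the visit list of Section 9.6.1, the factor would be 0.64.

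**4. Illustrations.** The documents give no effect of coaching frequency, so w − m is assumed throughout. With w = 1:

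| m | Bias | Apparent effect of a drug gain of 0.25 |
|---|---|---|
| 0.90 | −0.07 | +0.18 |
| 0.75 | −0.18 | +0.08 |
| 0.50 | −0.35 | −0.10 |
| 0.25 | −0.53 | −0.28 |

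With β₁ = 1 and a slope loss of 0.4 at month 6 (m = 0.6), the months 2–8 slope is 0.7 + 0.18 = 0.88:

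| γ₁ | Open-label slope difference | Placebo-arm bend (0.6 + γ₁ − 0.88) | Between-arm difference in slope change |
|---|---|---|---|
| 0 | 0 | −0.28 | 0 |
| 0.5 | 0 | +0.22 | 0.5 |
| 1.0 | 0 | +0.72 | 1.0 |

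The last column follows because any change k shared by both arms cancels: (γ₁ + k) − k = γ₁.

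**5. Precision.** This is ordinary least squares at the seven visits, one series per arm, residual error σ only. The standard error of the between-arm difference in slope change at month 8 is 0.445σ, with or without a month-6 knot common to both arms. In a single arm, adding the knot raises it from 0.31σ to 0.70σ, about 2.2-fold.

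**The case against.** A reader might infer that the open-label contrast is zero whether or not the drug works, without condition. The documents do not support that. It needs a constant, persistent slope gain that is equal in both arms after month 8. Section 9.6.1 leaves the intercept free and contemplates catch-up, and the restart at 25 mg BID is a dose decrease for AFQ056-arm children who were on higher doses. Either can make the difference non-zero. The catch-up sentence is also coherent if it means that the placebo arm's rate rises to match the other arm's.

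A reader might also infer a fourfold confounding of the placebo-arm comparison. The fourfold figure is the step at month 6; the compared periods differ threefold, and two months of monthly coaching fall before AFQ056 starts. Nor are sessions the child's exposure: they train the parent, who goes on delivering the intervention. Parent fidelity and frequency of use are recorded and are to be analysed as the effective dose (Sections 5.1, 5.4 and 6.3.14). That stands, but Section 9.6 gives no model in which the measure enters.

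Finally, one might read the blinded-setting phrase in Section 3 as simply false. Section 2.1 keeps the original assignment blinded during the extension until the last subject completes the placebo-controlled period and the data are locked. Families know that the current drug is active, but not whether the child has switched from placebo. The phrase needs clarifying, not deleting.

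The plan's defence that these analyses are exploratory, with a formal analysis plan still to come (opening of Section 9), limits the severity. It does not make the open-label contrast answer the stated purpose.

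**Conclusion.** The point holds in a conditional form. Under Equation 1 the open-label slope difference has expectation zero for any γ₁ and is uninformative about efficacy. It departs from zero only through catch-up in level (up to −γ₁ for full linear catch-up by month 16) or the AFQ056 arm's dose restart. The catch-up sentence is wrong if it refers to level, because closing a gap requires different slopes.

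The placebo-arm contrast is partly confounded, with bias −0.7(w − m) of unknown size. If less coaching slows learning, the bias runs against the drug; knowledge of active treatment could offset or reverse it.

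These results assume linear change and additive drug and coaching effects. The cancellation between arms needs the coaching effect to be the same in both; it would fail if the drug's gain depended on coaching intensity. The month 0–8 primary analysis is not affected.

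**What to change.** 1. In Section 9.6.1, state that similar open-label slopes are uninformative about efficacy and that catch-up in level means a steeper placebo-arm slope.
2. For extension purpose 3 and objective 1.4.4, add one exploratory longitudinal model over months 2–16 in both randomised arms, using every scheduled visit including month 6. Give it a month-6 knot common to both arms and arm-specific slope changes at month 8. The target is the slope change at month 8 in the former placebo arm minus that in the AFQ056 arm. Report the arm difference in level at month 16 beside it, with a sensitivity analysis using open-label visits from month 10.
3. In the placebo-arm model of Sections 9.6.1 and 9.6.3, add the month-6 knot or the parent-fidelity measure already collected.
4. In Section 3, say that original assignment stays blinded while the current drug is known to be active.

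**Cost.** Text and programming only; the visits are already scheduled. Four limits should be stated. The between-arm contrast is less precise than a single-arm slope change (0.445σ against 0.31σ above). It equals the blinded slope gap minus the open-label gap, so it is not independent of the primary result. The AFQ056 arm's dose restart at month 8 may affect it. Later enrolees have a shortened extension or none (Synopsis, Section 3), which reduces the data after month 8.

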take into account differential responsiveness and the known inter-child variability in drug levels with AFQ056, and allow use of the maximum tolerated dose (MTD) where MTD is defined as the maximum tolerated dose of the available dose levels in the protocol, which is felt likely to be most effective. There will be a 4-month single-blind placebo lead in after screening assessments during which subjects will have therapy treatments as usual to control for the effects of the language intervention. The placebo lead-in will also control for placebo effects which are prominent in clinical trials in FXS. This will be followed by an 8-month placebo-controlled phase in which 100 subjects with FXS will have AFQ056 baseline assessments and be randomized 1:1 to AFQ056 or placebo. Dose titration to MTD starting at 25 mg AFQ056/matching placebo will occur over 2 months and then subjects will have language intervention baseline assessments and initiate the language intervention, remaining on a stable AFQ056/placebo dose for the next 6 months. After 8 months of treatment in the placebo-controlled phase (6 months of language intervention), all subjects will have final assessments and will enter the open label extension and be treated with active drug according to the same schedule as in the placebo-controlled phase with 2 months of flexible dose titration to the MTD followed by a period of stable treatment. The duration of the stable treatment will depend on when the subject was enrolled into the study; those enrolled prior to June 15-30, 2019 will receive a 6-month period of stable treatment, and the open label extension may be shortened on a sliding scale for those enrolled after June 15, 2019, such that their treatment including weaning, if necessary, will end before August 31, 2021, with the exact length of the stable treatment period in the extension being determined by how long after June 15 they enroll and what dose of drug they are receiving in the open label treatment period (higher doses will have a longer weaning period of maximally 2 weeks for those on 75-100 mg BID, but 1 week for 50 mg BID, and no weaning period for lower doses). The total duration of the stable treatment for those enrolled after June 15, 2019 will range from 6 months to no open label extension, depending on the number of months after June 15, 2019 the subject is enrolled into the study. As such, some subjects will have an acute dose decrease if they were on a dose of 50-100 mg BID of active drug in the initial phase but experience from the Pediatric PK study conducted previously suggests that children can stop AFQ056 without withdrawal symptoms and the dose decrease and titration in the open label extension are unavoidable to maintain the blind of the study through the completion of the placebo-controlled period by the final participant. The open-label extension will allow all children a period of active drug exposure to make recruitment feasible, despite the long placebo period, and will allow additional collection of long-term safety data. Subjects will continue the language intervention through the extension phase to gain additional data on long-term effects of the combination of AFQ056 and the language intervention on developmental trajectory and the ERP biomarker.

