#### **Inclusion Criteria**

1. Age 32 months to 6 years inclusive at Screening (visit 1).
2. Has a documented *FMR1* full mutation.  
\*\*Note\*\* Presence of mosaicism is allowed.
3. DQ<75 calculated from the Mullen Scales of Early Learning at time of screening.
4. Parent or legal guardian is available and able to communicate well with the investigator, comply with study requirements and provide written informed consent.  
\*\*Note\*\*The parent or legal guardian who will be signing consent form, should be the individual administering the language intervention.
5. English is the primary language spoken in the home and the subject's first language is English.
6. Meet criteria indicating evidence of intentional communication based on parent interview via a communication eligibility screening tool.  
\*\*Note\*\* On the Eligibility Screening Tool – Communication, the child must have at time of screening:

AFQ056 for Language Learning in Children with FXS

Version v15

Version date 02/03/2021

- a) Section 1: Answer of YES; the child uses at least 5 spoken words to label items on a daily basis.
- OR
- b) Section 2: At least 3 YES answers to items 1-10 if child does not have at least 5 spoken words.

7. Produces 3 or more intentional acts of communication on the structured portion of the Weighted Communication play sample at time of screening.

\*\*Note\*\* Subjects are permitted to use augmentative communication devices throughout the study if the device is the subject's primary form of communication and the device has been prescribed for the subject by an SLP.

8. Stable behavioral and other therapy regimen for 30 days prior to screening.

\*\*Note\*\* Patients will be allowed to continue their standard-of-care therapies throughout the trial but these will not be changed during the placebo lead-in or placebo-controlled portion of the trial, outside of standard changes occurring from school schedules.

9. Stable dosing of all concurrent psychotropic medications except stimulants for at least 60 days prior to screening. Due to the very short half-life of stimulants (specifically methylphenidate and amphetamine variants), a stable regimen of these medications is required for 2 weeks only.

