In order to be able to relate the primary outcomes of improved language and communication as measured in a structured and coded play-based assay and normalization of auditory ERP to general development and behavior in FXS over the relatively long time course of the study, secondary outcomes will track domains of 1) cognitive development (Mullen Scales of Early Learning), adaptive development (Vineland Adaptive Behavior Scale), behavioral development (Aberrant Behavior Checklist – FX Version) eye tracking (biomarker of social engagement), language development (MacArthur Bates Communicative Development Inventory, Expressive Vocabulary Test, Peabody Picture Vocabulary Test, Visual Analog Scale for Language), and global function (CGI-I, CGI-S). The study will explore molecular measures of the translational pathway regulated by FMRP, including ERK, AKT, S6 kinase, APP, and MMP9 activities and phosphorylation (when applicable) state, to see if a molecular biomarker linked to clinical improvement can be identified.

This trial will **not only** address the impact of AFQ056 on language learning in young children with FXS, hence providing the first true test of the mGluR theory of intellectual disability in FXS by using a learning/plasticity model, but it will **also** test formally the effects of the language intervention itself in the largest group than has been studied to date, and will test whether abnormal auditory ERP can be a readout for improvement in language and speech sound processing and development related to either the language intervention itself, or the combination of the language intervention and AFQ056. Thus, important information will be generated even in the absence of a drug effect.

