At all visits, the following will be done: an interim history, vital signs, weight, height, a physical and neurological exam, adverse event review, suicidality review, dosing diary/compliance review, concomitant medication/therapy review, language intervention monitoring/review, and inclusion/exclusion criteria review will be done.

[figure not shown]
- The 8 month (visit 9) assessments will serve to evaluate whether AFQ056 was able to amplify language and communication progress over 6 months in a language intervention.
- The 4 and 6 month (visits 7 and 8) assessments will allow an evaluation of the trajectory over time of effects of the language intervention and any potential additional drug effect and whether it occurs early or there is a progressive building of the effect(s) over time.
- The 4 month assessment will also allow some data to be collected in the case of families who are not able to sustain the language intervention with the same intensity in the later part of the 6 months as opposed to the early months. It is not expected this will be a frequent problem, however.

The 4 month placebo lead-in will allow for placebo effects to stabilize, and for the group ultimately randomized to placebo, there will be 6 months (4 month placebo lead-in + 2 months of placebo dose titration after randomization) of placebo treatment without the language intervention, which will allow this group to serve as a treatment-as usual/medication placebo control group for the 6 month language intervention placebo group, thus allowing the effects of the language intervention alone in FXS to be quantified.

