In the placebo group, LMM analyses will be used to compare trajectory of developmental progress during the 6 months on placebo alone and during the 6 months receiving the language intervention while on placebo. This will generate information about the efficacy of the language intervention alone. Trajectory of developmental progress in these two periods will be compared with trajectory in the 8 months after the placebo group begins AFQ056 in the open label extension.

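### The language intervention is assessed by an uncontrolled change of slope in the placebo arm, which cannot formally test it and leaves out the AFQ056 arm's lead-in data

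*Combined protocol and SAP*

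**What the plan says.** The analysis is set out in section 9.6.1: "In the placebo group, LMM analyses will be used to compare trajectory of developmental progress during the 6 months on placebo alone", against the 6 months on placebo with the intervention. The paragraph ends: "This will generate information about the efficacy of the language intervention alone". Section 9.6.3 repeats the restriction among the exploratory hypotheses ("Longitudinal analysis to determine whether the rate of change in language, functional, or biomarker responses in the group assigned to placebo"), with inflection points at months 2 and 8.

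The pre-intervention period is "6 months (4 month placebo lead-in + 2 months of placebo dose titration after randomization) of placebo treatment without the language intervention" (section 3). All children in both arms begin the intervention at month 2. The Synopsis states that "100 subjects with FXS will have AFQ056 baseline assessments and be randomized 1:1 to AFQ056 or placebo". Section 4.4.1 adds that children who withdraw during the lead-in are replaced, so all 100 randomised children will have completed it.

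The strength of the claim varies. Section 1.4.4 is listed among the exploratory objectives. Section 3 describes the design as "thus allowing the effects of the language intervention alone in FXS to be quantified". Section 9.3 (Placebo Lead-In) says that comparing the two periods will define what the intervention does. Section 2.1 says the trial will "test formally the effects of the language intervention itself".

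Inclusion criterion 7 requires that the child "Produces 3 or more intentional acts of communication on the structured portion" of the same play task that supplies the first outcome score.

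**The concern.** The intervention is fully tied to time in study. Any other reason for the rate of communication growth to change around month 2 is read as an effect of the intervention. The protocol gives one such reason itself: section 2.1 describes ages 3 to 6 as a transition period for language in fragile X. Repeated exposure to the play task, a placebo response that builds or fades, and selection on the screening sample are others.

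This matters because section 2.1 presents the result as knowledge gained even if the drug does nothing. If the drug comparison is null, this analysis may become the trial's main message, and the current wording would let an uncontrolled change be reported as a formal test.

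Separately, both arms go through the same placebo lead-in before randomisation, but only the placebo arm's lead-in is given a role in the analysis.

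**Working it through.** **The plan's own figure.** There is none for this comparison. Section 9.8 (50 per arm, 80% power) concerns only the drug contrast, and it does not give the variance components needed to reproduce it.

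**Inputs.**
- Weighted communication score at months -4, 0, 2, 4, 6 and 8 (Table 7 and section 6.3.9; there is none at month -2).
- 50 children per arm (Synopsis).
- Assumed, because the documents give no fragile X values: total SD 10.2 to 17.9 (a non-fragile-X cohort cited in section 6.3.9), intraclass correlation 0.5 to 0.85, and SDs of slope and of slope change of 0 to 1 point per month.

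**Unused data.** Lead-in scores: 100 children × 2 = 200, of which 100 (50%) are from the AFQ056 arm. Drug-free scores up to month 2: 150 placebo + 100 AFQ056 = 250, so 40% are unused.

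**Weights.** Model: intercept, slope, and slope change at month 2, with random effects on all three. With complete data the placebo-arm estimate of the slope change is a weighted sum of the mean scores:

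| Month | -4 | 0 | 2 | 4 | 6 | 8 |
|---|---|---|---|---|---|---|
| Weight | +0.195 | -0.086 | -0.227 | -0.094 | +0.039 | +0.172 |

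The weights and their products with month both allow for a constant slope, so linear maturation contributes nothing.

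**Precision.** The squared weights sum to 0.137, so SE² = (0.137σ² + τ²)/50, where σ² is the residual variance and τ the SD of slope change. Example: SD 10.2, correlation 0.7, both slope SDs 0.5. Then σ² = 10.2² × 0.3 = 31.2 and SE = √[(0.137 × 31.2 + 0.25)/50] = 0.301. Adding the AFQ056 arm's months -4 and 0 by generalised least squares gives 0.272, about 10% smaller. Over the whole assumed range the SE falls by 4% to 11% (variance by about 8% to 21%).

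**Selection at screening.** Simulation with an assumed mean of 6 to 12 acts (SD 5 to 9) puts the screening excess from the three-act rule at 0.19 to 0.43 acts. At weight 1 per act:
- 0.195 × 0.19 = 0.04 points per month
- 0.195 × 0.43 = 0.08 points per month

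Both favour the intervention. Acts scored at weight 2 would double these.

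**Change in the natural rate.** In the cited cohort the score rises from 14.4 to 22.1 between 14 and 30 months of age: 7.7/16 = 0.48 points per month. Suppose the intervention does nothing and the natural rate increases smoothly between the midpoints of the two periods (months -1 and 5). With correlation 0.70 to 0.85 and both slope SDs 0.5:

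| Natural rise | Spurious slope change (points/month) | Two-sided 5% test rejects |
|---|---|---|
| none | 0 | 5% |
| 50% | 0.26 | 8% to 23% |
| 100% | 0.53 | 17% to 67% |

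These are illustrations. The documents do not bound the true change.

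**Direction of practice and placebo effects.** A lasting 1-point gain present from month 0 onward moves the slope change by -0.086 - 0.227 - 0.094 + 0.039 + 0.172 = about -0.195, against the intervention. The same gain arriving at month 4 moves it by -0.094 + 0.039 + 0.172 = +0.117, in its favour.

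**The case against.** The strongest reply is that this is a disclosed, exploratory compromise. Section 9.3 weighs three- and four-arm designs. It rejects the first because families would know whether they had the intervention, and the second because it needs at least 160 participants and is not critical to the drug hypothesis. The lead-in was added for this purpose. The sentence in section 9.6.1 promises only information, no alpha or power attaches to it, and section 9.6.3 already plans the inflection at month 2. Section 5.1 also plans to relate parental fidelity and use to child outcomes, so this is not the only look at the intervention. All of that stands. It explains why there is no control but does not supply one, and it does not support the wording in sections 2.1 and 9.3.

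A reader might infer that the analysis would simply report maturation as efficacy. The documents do not support that. The comparison is slope against slope within child, and section 6.3.9 states that the measure grows linearly over these stages. What remains is an assumption that needs stating, since section 9.5.1 concedes that data on this measure in fragile X are lacking.

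A reader might also infer that every bias favours the intervention. Early practice gains or a placebo response building during the lead-in would work against it.

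Nor does leaving out half of the lead-in scores mean a large loss: the gain from using them is small, and pooling creates no concurrent control.

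**Conclusion.** The concern holds in a limited form. The planned comparison is a reasonable exploratory description of how the rate changes when the intervention begins. It cannot formally test or define the intervention's effect, because no group goes without it after month 2. The identifiable selection bias is small (about 0.04 to 0.08 points per month, resting on assumed act means and SDs). Bias from a change in the natural rate could be larger but cannot be bounded from the documents. Using the AFQ056 arm's lead-in is justified by randomisation and would reduce the standard error by 4% to 11% under the assumed variances. Nothing here touches the randomised comparison of AFQ056 with placebo.

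**What to change.** Keep the month-2 knot of section 9.6.3, but fit one piecewise mixed model in which months -4 and 0 from all 100 children inform a common lead-in slope and months 0 to 8 come from the placebo arm. Report the slope change with its confidence interval as an exploratory, uncontrolled change in rate associated with the intervention, and state that the reading assumes linear maturation.

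Add a sensitivity analysis without the screening score. Pooling does not remove the selection effect, since both arms were screened by the same rule. This check is much less precise: with months 0 to 8 only, the squared weights sum to 0.625, so in the example above the placebo-arm SE becomes √[(0.625 × 31.2 + 0.25)/50] = 0.63 against 0.30. It should serve as a check, not as the main estimate.

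Replace the efficacy wording in section 9.6.1, the formal-test wording in section 2.1 and the corresponding sentence in section 9.3 (Placebo Lead-In) with that description. Section 9 says a formal analysis plan is still to be developed, and the model can go there. The cost is a slightly weaker claim and a little more analysis; no data collection changes.
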